4.3. Variables

Variable	Role	Data source(s)	Operational definition
Index date	Study period	Case report form	Inform consent date
Index year	Study period	Case report form	Inform consent date
Pre-Oxbryta	Study period	Case report form	Baseline: any assessments within 12 months before receiving first dose of Oxbryta® (Voxelotor)
Post-Oxbryta	Study period	Case report form	Follow-up period for up to 5 years after the first dose of Oxbryta® (Voxelotor)
End of Treatment	Study period	Case report form	Captured from end of treatment form
End of Study	Study period	Case report form	Captured from end of study form
Age	Demographics	Case report form	Age at first dose of Oxbryta
Sex	Demographics	Case report form	Captured from the inform consent and eligibility form
Race/Ethnicity	Demographics	Case report form	Captured from the inform consent and eligibility form

SCD genotype	SCD disease history	Case report form	Captured from SCD disease history form
Hydroxyurea use	SCD disease history	Case report form	Captured from SCD disease history form
Height	Baseline characteristics	Case report form	Captured from Physical examination form
Weight	Baseline characteristics	Case report form	Captured from Physical examination form
Pre-Oxbryta SCD complications	Medical history	Case report form	Captured from Pre-Oxbryta treatment form
Concomitant Medications	Concomitant Medications	Case report form	Captured from concomitant medications form
Hemoglobin	Effectiveness endpoint measures - Hematology	Case report form	Captured from laboratory assessment-Hematology form
Reticulocyte count (%)	Effectiveness endpoint measures - Hematology	Case report form	Captured from laboratory assessment-Hematology form
Reticulocyte count (absolute)	Effectiveness endpoint measures - Hematology	Case report form	Captured from laboratory assessment-Hematology form
White blood cells (WBC)	Effectiveness endpoint measures - Hematology	Case report form	Captured from laboratory assessment-Hematology form
Aspartate Aminotransferase (AST)	Effectiveness endpoint measures - Hematology	Case report form	Captured from laboratory assessment-Hematology form
Alanine Aminotransferase (ALT)	Effectiveness endpoint measures - Hematology	Case report form	Captured from laboratory assessment-Hematology form
Bilirubin (Total)	Effectiveness endpoint measures - Chemistry	Case report form	Captured from laboratory assessment-Chemistry form
Bilirubin (Direct)	Effectiveness endpoint measures - Chemistry	Case report form	Captured from laboratory assessment-Chemistry form

Bilirubin (Indirect)	Effectiveness endpoint measures - Chemistry	Case report form	Captured from laboratory assessment-Chemistry form
Ferritin	Effectiveness endpoint measures - Chemistry	Case report form	Captured from laboratory assessment-Chemistry form
Albumin Creatinine Ratio (ACR)	Effectiveness endpoint measures – Renal function	Case report form	Captured from laboratory assessment- Renal function form
GFR	Effectiveness endpoint measures – Renal function	Case report form	Captured from laboratory assessment- Renal function form
Creatinine (Serum)	Effectiveness endpoint measures – Renal function	Case report form	Captured from laboratory assessment- Renal function form
Serum cystatin C	Effectiveness endpoint measures – Renal function	Case report form	Captured from laboratory assessment- Renal function form
Estimated eGFR	Effectiveness endpoint measures – Renal function	Case report form	Captured from laboratory assessment- Renal function form
Transfusions	Safety endpoint measures	Case report form	Captured from transfusions form
Patient Global Impression of Change (PGI-C)	Effectiveness endpoint measures	Case report form	Captured from Patient Global Impression of Change (PGI-C) form
Clinical Global Impression of Change (CGI-C)	Effectiveness endpoint measures	Case report form	Captured from Clinical Global Impression of Change (CGI-C) form
Pregnancy Testing and Fertility	Safety endpoint measures	Case report form	Captured from Pregnancy Testing and Fertility form
SCD Complications/Adverse Events	Safety endpoint measures	Case report form	Captured from SCD Complications/Adverse Events Question form
Pregnancy	Safety endpoint measures	Case report form	Captured from Pregnancy Notification and Outcome forms
Oxbryta Physician Administration	Exposure measures	Case report form	Captured from Oxbryta Physician Administration form

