9.7. Study Data Collection

Data on participants will be collected at regular intervals and entered into the EDC system by study personnel at the study site beginning with their first dose of commercial Oxbryta® (Voxelotor). Data collection will include those data that are recorded in the participant's medical records/other secondary data sources and based on assessments performed as part of the participant's SOC. Study data that are not available in medical records or other secondary data sources will not be solicited from participants. The data to be collected in this study and target timepoints for data collection and entry are specified in the schedule of activities (SOA) in [Appendix 1](#).

There are not any required study procedures or assessments beyond the SOC. The SOA should be used as a guide for what data to enter and not for what assessments to perform. Therefore, if an assessment listed in the schedule of activity of the protocol is considered standard of care, the sites are asked to enter the assessment result into the study database. If an assessment is not conducted as SOC, the sites can just leave the relevant data fields blank.

Since Health-Related Quality of Life Measures (PROMIS, PGIC, NPRS and CGIC) are not commonly conducted as SOC, in order to allow important quality-of-life data to be gathered in the registry, questionnaires are provided to the sites and participants, and we recommend (but not require) the sites to perform these assessments.

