10.3.6. Effectiveness Data

10.3.6.1. Clinical Outcomes

10.3.6.1.1. Laboratory Assessments

The following data will be recorded on the CRF:

For pre-Oxbryta® (Voxelotor) Treatment Visits, only the most recent results from regularly scheduled outpatient visit will be entered.

For post-Oxbryta® (Voxelotor) Treatment Regularly Scheduled Outpatient Visits, all available results during the data collection period will be entered.

For post-Oxbryta® (Voxelotor) Acute Visits (Emergency Department, Hospitalization, Acute Pain/Infusion Center), only the results on the day of presentation (or first available results during the visit) and day of discharge will be entered, if available.

The following data from the most recent results will be recorded in the CRF:

- Hb (including % HbF at baseline and all follow up visits), white blood cells (WBC), absolute neutrophil count (ANC), mean corpuscular volume (MCV), mean corpuscular hemoglobin concentration (MCHC), Platelets, aspartate aminotransferase (AST), alanine aminotransferase (ALT), and lactate dehydrogenase (LDH).
- Hemolysis measures, including % reticulocytes, absolute reticulocytes, bilirubin (total, direct, and indirect)
- Measures of iron overload (ferritin, iron, TIBC, T2*MRI)
- Creatinine (Serum)
- Albuminuria (urine albumin/creatinine ratio [ACR])
- Hemoglobinuria (urine dipstick positive for blood +1 or greater and ≤ 2 RBC by high power field)
- Serum cystatin C
- eGFR calculated using CKD-EPI equation

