3.2 Effectiveness Endpoint Measures

- Change from pre-Oxbryta® (Voxelotor) treatment period in the following hematologic parameters:
 - Hb
 - Hemolysis measures, including % reticulocytes, absolute reticulocytes, bilirubin (total, direct, and indirect)
 - Measures of iron overload, including ferritin, T2-weighted magnetic resonance imaging (T2*MRI)
- Change from pre-Oxbryta® (Voxelotor) treatment period in renal function, as measured by the following:
 - Creatinine (Serum)
 - Albuminuria (urine albumin/creatinine ratio [ACR])
 - Hemoglobinuria (urine dipstick positive for blood +1 or greater and ≤ 2 RBC by high power field)
 - Serum cystatin C

PFIZER CONFIDENTIAL

CT24-WI-GL03-RF03 3.0 *Non-Interventional Statistical Analysis Plan*
for Secondary Data Collection Study

- Estimated glomerular filtration rate (eGFR) calculated using the Chronic Kidney Disease Epidemiology Collaboration (CKD-EPI) equation
- Rate of significant SCD complications, for example acute pain crisis, acute chest syndrome (ACS), priapism, stroke, and transient ischemic attack (TIA), chronic or end stage kidney disease, iron overload, leg ulcers, cardiac malfunction, and pulmonary hypertension (PH)
- Treatment initiation or modification of SCD-related medications (eg, hydroxyurea, crizanlizumab, L-glutamine, opioids [in daily morphine equivalents], iron chelating agents, erythropoiesis-stimulating agents [ESAs], nonsteroidal anti-inflammatory drugs [NSAIDs], folic acid, and penicillin)
- Change from pre-Oxbryta® (Voxelotor) treatment period in HCRU: rate of outpatient visits (including infusion center, acute care, or telemedicine visit), emergency department (ED) visits, hospitalizations (including total length of stay and time in intensive care unit [ICU], if applicable), acute and chronic RBC transfusions, home oxygen supplementation, and renal dialysis
- Change from pre-Oxbryta® (Voxelotor) treatment period in the following HRQoL measures:
 - Patient-Reported Outcomes Measurement Information System (PROMIS) 42 item (adults) and 39 item (children/ adolescents)
 - Patient Global Impression of Change (PGIC)
 - Clinical Global Impression of Change (CGIC)
 - Other measures: Acute pain intensity as measured by Numerical Pain Rating Scale (NPRS) and any objective measure of exercise tolerance.

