- Change from pre-Oxbryta treatment period in the following Chemistry parameters corresponding to treatment with Oxbryta® (Voxelotol):
 - Ferritin

Analysis: Observed and change from pre-Oxbryta treatment period on ferritin will be summarized descriptively ([Section 4.7](#)) by visit.

- Change from pre-Oxbryta® (Voxelotol) treatment period in renal function:
 - Creatinine (Serum)
 - Albuminuria (urine albumin/creatinine ratio [ACR])
 - Hemoglobinuria (urine dipstick positive for blood +1 or greater and ≤ 2 RBC by high power field)
 - Serum cystatin C
 - Estimated eGFR calculated using the CKD-EPI equation

Analysis: Observed and change from pre-Oxbryta treatment period on Creatinine (Serum), Albuminuria, Hemoglobinuria, Serum cystatin C and eGFR will be summarized descriptively ([Section 4.7](#)) by visit

- Rate of SCD complications including acute pain crisis, acute chest syndrome

(ACS), priapism, stroke, and transient ischemic attack (TIA), chronic or end stage kidney disease, iron overload, leg ulcers, cardiac malfunction, and pulmonary hypertension (PH) and RBC transfusions.

Analysis:

The number and percentage of participants with SCD complications including acute pain crisis, ACS, priapism, stroke, chronic or end stage kidney disease iron overload, leg ulcers, cardiac malfunction and PH and RBC transfusions will be summarized by SOC and PT throughout the treatment period.

The annualized incidence rate of SCD complications including acute pain crisis, ACS, priapism, stroke, chronic or end stage kidney disease iron overload, leg ulcers, cardiac malfunction and PH and RBC transfusions will be summarized by SOC and PT throughout the treatment period.

- **PGIC**

PGIC includes 7 response categories: Very much improved, much improved, minimally improved, no change, minimally worse, much worse and very much worse.

Analysis: The PGIC will be summarized as numbers and percentages by visit for each response category.

- **CGIC**

CGIC includes 7 response categories: Very much improved, much improved, minimally improved, no change, minimally worse, much worse and very much worse.

Analysis: The CGIC will be summarized as numbers and percentages by visit for each response category.

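### eGFR is sourced from the CRF with CKD-EPI named but no version, marker or derivation rule, so a switch of equation within a participant can appear as change in eGFR

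*SAP*

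**What the plan says.** **Source of the value.** The variables table in SAP 4.3 has separate rows for GFR, serum creatinine, serum cystatin C and Estimated eGFR. Each has the case report form as data source and the same operational definition: "Captured from laboratory assessment- Renal function form". Nothing marks eGFR as derived, and nothing says how the GFR and Estimated eGFR rows differ or which of them enters the renal table. Protocol 10.3.6.1.1 opens its list of laboratory items with "The following data from the most recent results will be recorded in the CRF" and includes in it "eGFR calculated using CKD-EPI equation".

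**Equation.** SAP 3.2 lists the endpoint as "Estimated glomerular filtration rate (eGFR) calculated using the Chronic Kidney Disease Epidemiology Collaboration (CKD-EPI) equation". SAP 4.7.3 repeats it as "Estimated eGFR calculated using the CKD-EPI equation". Neither gives a version, states the marker (creatinine, cystatin C or both), or says who does the calculation.

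**Setting.** Protocol 9.7 limits collection to data in medical records or other secondary sources and "based on assessments performed as part of the participant's SOC", and adds: "There are not any required study procedures or assessments beyond the SOC". No central laboratory or eGFR harmonisation step is described. The only exclusion thresholds in SAP 4.7.3 are for absolute reticulocytes and ferritin.

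**Analysis.** SAP 4.7.3 provides that "Serum cystatin C and eGFR will be summarized descriptively" by visit, as observed values and as change from the pre-Oxbryta period. The output is Table 15.2.4.

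**The concern.** eGFR is not measured. It is a formula applied to creatinine (or cystatin C), age and sex, and its value depends on the version used. A plan that names a family of equations but sources the number from a form leaves the version to whoever filled in or printed that number. With local laboratories and a span of up to 6 years (12 months before plus 5 years after first dose), the version behind a participant's pre-Oxbryta value need not be the version behind a later one. If it is not, the table can show a change in eGFR when creatinine has not moved.

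Renal function is one of the few effectiveness areas kept in the abbreviated report, and there is no concurrent control group. A step of this kind would therefore sit directly in a within-participant change summary.

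**Working it through.** The plan gives no eGFR figure, SD or equation coefficients, so there is no stated number to reproduce. The check is in three steps.

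**1. When does a version difference create change?** Let p be the share of participants whose version differs between the pre-Oxbryta and follow-up values, d the relative difference between versions at the same creatinine, and B the baseline eGFR. None of the three is in the documents; all are assumptions. With creatinine unchanged:

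artefact in mean change = p × d × B

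With B = 120 mL/min/1.73 m²:
- p = 0: 0 for any d, even if sites use different versions.
- p = 0.25: 0.25 × 0.02 × 120 = 0.6; with d = 0.10, 3.0; with d = 0.15, 4.5.
- p = 1: 2.4, 12 and 18 for the same three values of d.

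A constant difference between sites cancels within a participant, apart from rescaling any true change. Only a switch within a participant creates a false step. The sign depends on which version came first.

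**2. How large could d be?** Assumption: a switch from the CKD-EPI 2009 to the CKD-EPI 2021 creatinine equation. The coefficients are assumed here, not taken from the documents. Scr is serum creatinine in mg/dL.

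- 2009: 141 × min(Scr/κ,1)^α × max(Scr/κ,1)^-1.209 × 0.993^age, × 1.018 if female, × 1.159 if the race coefficient is applied; κ = 0.7 (female) or 0.9 (male), α = -0.329 or -0.411.
- 2021: 142 × min(Scr/κ,1)^α × max(Scr/κ,1)^-1.200 × 0.9938^age, × 1.012 if female; same κ, α = -0.241 or -0.302.

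Man aged 35, Scr 0.9: both min and max terms equal 1. For 2009, 141 × 0.993^35 = 110.3, and × 1.159 = 127.8. For 2021, 142 × 0.9938^35 = 114.2.

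| Unchanged creatinine | 2009 with coefficient | 2009 without | 2021 | Step, with | Step, without |
|---|---|---|---|---|---|
| Man 35, 0.9 | 127.8 | 110.3 | 114.2 | -13.6 (-11%) | +4.0 (+4%) |
| Woman 35, 0.7 | 130.1 | 112.3 | 115.6 | -14.5 (-11%) | +3.3 (+3%) |
| Man 30, 0.8 | 138.9 | 119.9 | 122.1 | -16.8 (-12%) | +2.2 (+2%) |
| Man 50, 1.0 | 101.3 | 87.4 | 91.7 | -9.6 (-9%) | +4.3 (+5%) |

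(Steps are from unrounded values.) Across plausible adult values the step is roughly -9% to -17% with the coefficient and -4% to +6% without. The corners of a wider grid reach -19% and -6% (man aged 18, creatinine 0.4) and -8% and +7% (man aged 65, creatinine 1.5).

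For scale, a real rise in creatinine from 0.8 to 0.9 in a man aged 30, with one version throughout, changes eGFR by -4.3 (2021) to -6.6 (2009 with coefficient).

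**3. Effect on a mean.** For the man aged 30, p × step is:
- p = 0: 0.
- p = 0.10: -1.7 with the coefficient, +0.2 without.
- p = 0.25: -4.2 and +0.6.
- p = 0.50: -8.4 and +1.1.

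With one fixed version applied to every record, p = 0 and the artefact is 0 for any d and B.

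**The case against.** Several stronger readings are tempting, and the documents do not support them.

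- **That eGFR will not be recomputed.** A reader might infer this from the CRF source in SAP 4.3. But the definition there is generic: it also covers ACR, creatinine and cystatin C. The endpoint text says eGFR is calculated with CKD-EPI. Neither document says recomputation will or will not happen. What stands is that no rule tells the programmer to do it or which version to use.
- **That differences between local laboratories will appear as change.** Constant differences cancel within a participant. A switch is needed, and nothing in the documents shows one.
- **That such a step could not be told from a drug effect.** SAP 4.7.3 also summarises serum creatinine and cystatin C by visit. A fall in eGFR with flat creatinine would be visible, so there is a partial check. It only signals a problem and does not correct the eGFR columns.
- **That the kidney-disease events are affected.** Protocol 10.3.6.1.8 describes chronic or end-stage kidney disease by a GFR below 60, and under the step 2 assumptions (coefficient applied before the switch) a man aged 45 with creatinine of 1.47 to 1.58 mg/dL would cross 60 on the switch alone. But SAP 4.7.4 identifies SCD complications by a Yes on the complications/AE form, and no step derives them from eGFR values. Recomputation would leave those event tables unchanged.

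It can also be said that the analysis is descriptive, for an abbreviated report with limited efficacy data, and that eGFR is one of five renal measures. That is correct: no test or error rate is at stake. It limits the weight of the point but does not remove the gap.

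**Conclusion.** The point holds in a conditional form. The plan sources eGFR from a form, names CKD-EPI without version, marker or calculating party, and leaves two eGFR-type rows undistinguished. Followed literally, it carries unharmonised local values into a change table that can span about 6 years. If a participant's equation version changes between the pre-Oxbryta value and follow-up, a step at unchanged creatinine can appear as change in eGFR in Table 15.2.4.

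The size cannot be taken from the documents. It is zero if nobody switches. Under the assumed 2009-to-2021 switch, a step for one adult can exceed that from a real 0.1 mg/dL rise in creatinine if the race coefficient was applied before, and is small if it was not. The effect on a mean then scales with a share of switchers that is unknown. This is a worthwhile, low-cost improvement to a descriptive endpoint. It does not show that the reported eGFR results are wrong.

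**What to change.** In SAP 4.3 and 4.7.3:

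1. Define adult eGFR as a derived variable, computed for every record from recorded serum creatinine, age at sample and sex with one fixed, stated CKD-EPI creatinine version. Any single version removes the switch artefact.
2. Use the derived value for adults in Table 15.2.4. Keep laboratory-reported GFR and eGFR as a listing, and say how those two rows differ.
3. Show participants under 18 separately, with their source or method stated. Participants from age 4 are eligible, and an adult-only derivation would otherwise drop them from the table.
4. State how age at sample is obtained, because SAP 4.3 defines age at first dose. Age at first dose plus elapsed time is enough: one year of age changes the 2021 value by about 0.6% (1 - 0.9938).

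**Cost.** One derivation; serum creatinine, age and sex are already collected. The downside is that adult visits with a reported eGFR but no creatinine leave the table, so the number lost should be reported.

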4.4. Data sources

The main data source is through the electronic data capture in the study, while secondary data sources may include insurance claims, electronic medical records, hospital administrative data, and specific rare disease databases. Data from C5341018 (RETRO) being used for participants who transferred from RETRO to this study.

4.5. Sample size and power calculations

The sample size is selected based on feasibility considerations to provide an estimation of the relationship between change in Hb and significant clinical events, for example VOCs and stroke that participants experience over the 5 years of the study. The total sample size of approximately 500 participants is expected to be enrolled. There is no formal sample size calculation for this study.

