9.11.2. Sample Size

The sample size is selected to provide an estimation of the relationship between change in Hb and significant clinical events, for example VOCs and stroke that participants experience over the 5 years of the study. The total sample size of approximately 500 participants is expected to be enrolled.

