9.11.3. Effectiveness Endpoint Measures Analyses

Baseline Demographic Characteristics:

Baseline demographic characteristics will be summarized descriptively.

Endpoints:

- Change from pre-Oxbryta® (Voxelotor) treatment period in Hb, hemolysis measures, measures of iron overload, and renal function over time will be summarized descriptively.
- Annualized rate of significant SCD-related clinical events, for example VOC, ACS, priapism, stroke, TIA, chronic or end stage kidney disease, iron overload, leg ulcers, cardiac malfunction, and PH will be calculated. The association between change in Hbhemolysis marker and rates of SCD-related clinical events will be evaluated.
- Rates of outpatient visits (including infusion center, acute care, or telemedicine visit), ED visits, hospitalizations, acute and chronic RBC transfusions, home oxygen supplementation, and renal dialysis will be summarized with a similar approach as incidences of SCD-related clinical events. The total cost associated with clinical interventions will be summarized descriptively.

- HRQoL measures over time will be summarized descriptively. Proportions of participants with improved HRQoL measures will be calculated and the associated 95% Clopper Pearson Exact confidence intervals will be constructed as appropriate.
- Rates of SCD-related clinical events, healthcare resource utilization, total cost associated with clinical interventions (if available) and HRQoL while on Oxbryta® (Voxelotor) treatment will be compared with the corresponding measures prior to the first dose of Oxbryta® (Voxelotor) treatment, as appropriate.

Subgroup analysis:

Similar comparisons may be performed between the subgroup of participants who discontinue Oxbryta® (Voxelotor) treatment but remain in the study and those participants who remain on Oxbryta® (Voxelotor).

Other subgroup or sensitivity analyses may be performed.

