4.2.1. Subgroups

- 1) Chronic pain:
 - a. Full analysis set for participants with chronic pain
 - b. Full analysis set for participants without chronic pain

Participants with chronic pain are defined to have at least one of following criteria during pre-Oxbryta or post-Oxbryta:

- SCD complications page: Avascular Necrosis, Chronic Pain; OR
- Non-SCD medical history page: Arthralgia, Arthritis, Neuralgia, Osteoarthritis, Osteonecrosis, Osteoarthritis, Rheumatoid arthritis, Spinal osteoarthritis; OR
- Concomitant medications page: BACLOFEN, GABAPENTIN, MELOXICAM, PREGABALIN, all “BUPRENORPHINE”, DULOXETINE, DULOXETINE HYDROCHLORIDE, METHADONE, METHADONE HYDROCHLORIDE, PREGABALIN.

- 2) Maximum increase from Pre-Oxbryta in Hb
 - a. Full analysis set for participants with > 1 g/dL maximum increase from Pre-Oxbryta in Hb during the study period

b. Full analysis set for participants with ≤ 1 g/dL maximum increase from Pre-Oxbryta in Hb during the study period

3) Full analysis set where participants had a non-missing Pre-Oxbryta SCD complication will be included in the analysis.

4) Full analysis set where participants who had a non-missing Pre-Oxbryta SCD complication or participants who had an adverse event reported in Pre-Oxbryta or Post-Oxbryta will be included in the analysis.

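### The SAP keeps the Hb-event relationship as the purpose of the sample but never estimates it; its only link is a pair of crude tables grouped by maximum Hb rise, and that grouping is biased

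*SAP*

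**What the plan says.** **Purpose.** According to SAP 4.5 the number of participants rests on feasibility, and the sample is meant "to provide an estimation of the relationship between change in Hb and significant clinical events". VOCs and stroke over five years are its examples. The section also states: "There is no formal sample size calculation for this study". Protocol 9.8 and 9.11.2 give the same purpose without the reference to feasibility.

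**Promised analysis.** Protocol 9.11.3 says that the association of change in Hb and hemolysis marker with "rates of SCD-related clinical events will be evaluated". The sentence is garbled there but reads cleanly under Statistical Methods in the Abstract. Neither place names a method.

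**Planned analysis.** SAP 4.2.1 defines one subgroup as "Full analysis set for participants with > 1 g/dL maximum increase from Pre-Oxbryta in Hb", taken over the study period, and a second with a maximum rise of 1 g/dL or less. SAP 4.7.5 plans the annualized acute pain crisis rate, pre- and post-Oxbryta, in each. The outputs are Tables 15.5.3 and 15.5.4. SAP 4.7 defines the rate as total events over total patient-years.

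**Scope.** SAP 4.7.3 describes an abbreviated report with limited efficacy data that focuses on hematologic and renal laboratory parameters and SCD-related clinical events. It explains why PROMIS was left out and does not mention the Hb-event association. The version history does not mention its removal either.

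**The concern.** A stated purpose and a protocol commitment have no matching analysis. Followed exactly, the SAP yields four crude rates for one event type (pre and post in each of two groups) and no measure of how event rates vary with Hb change. Stroke, which SAP 4.5 names itself, is never tabulated by Hb.

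Readers will probably use Tables 15.5.3 and 15.5.4 as the answer, because nothing else in the report links the two quantities. If the grouping is distorted by event timing, length of follow-up and testing frequency, the difference between the tables cannot be read as the effect of a larger Hb response.

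**Working it through.** **1. The plan's own figure.** There is nothing to reproduce. The documents give no effect size, event rate, dispersion or precision target, and SAP 4.5 says there was no formal calculation. (The Abstract's Sample Size text says about 750; the other places say about 500.)

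**2. Every SAP analysis that uses Hb or SCD events.**

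| SAP place | What is produced | Links Hb to events? |
|---|---|---|
| 4.7.3, Hb | Observed value and change by visit | No |
| 4.7.3, SCD complications | Counts and annualized rates by organ class and preferred term | No |
| 4.7.5, VOC rate | Pre and post rates in two other populations | No |
| 4.7.5, Tables 15.5.3 and 15.5.4 | Pre and post acute pain crisis rates in each maximum-rise group | Indirectly |

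No between-group contrast, rate ratio, regression, interval or covariate adjustment is specified.

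**3. Three weaknesses of the maximum-rise grouping.**
- *Timing.* The maximum is taken over the whole study period, while post-Oxbryta events count from the first dose. A participant's group can be settled after the events being compared.
- *Acute-visit values.* Protocol 10.3.6.1.1 has Hb entered from acute visits at presentation and discharge. SAP 4.7.3 excludes values only for absolute reticulocytes and ferritin above set thresholds. An Hb raised by a transfusion given for an event could therefore place a participant in the upper group.
- *Number of values.* Protocol 10.3.6.1.1 enters only the most recent outpatient result before treatment but all available outpatient results after it. The maximum of many values is set against one baseline.

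The third can be sized. Assume no true Hb change and independent normal values with within-person SD s (an assumption; the documents give none). For one post-baseline value, P(rise > 1) = 1 − Φ(1/(s√2)). At s = 0.4 this is 1 − Φ(1.77) = 3.8%; at s = 0.8 it is 1 − Φ(0.88) = 18.8%. For more values, simulation with 200,000 participants per setting gives the chance of a maximum rise above 1 g/dL:

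| s (g/dL) | 1 value | 4 values | 8 values | 12 values |
|---|---|---|---|---|
| 0.4 | 3.8% | 11.4% | 17.7% | 22.3% |
| 0.6 | 11.8% | 29.7% | 41.5% | 48.7% |
| 0.8 | 18.8% | 42.5% | 55.6% | 62.7% |

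The Schedule of Activities has 4 post-baseline timepoints by month 12 and 12 by month 60, so a participant followed for five years is much more likely than one followed for a few months to enter the upper group by chance.

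**4. What an estimate could offer (illustration only).** Assume all 500 contribute, an SD of Hb change of 1.0 to 1.5 g/dL, 1 to 5 years of follow-up and negative-binomial dispersion k of 0.5 to 1.5. The standard error of the log rate ratio per 1 g/dL is about √[(1/(rate × years) + k)/(n × SD²)].
- Frequent event, widest case (1 per patient-year, 1 year, k = 1.5, SD 1.0): √(2.5/500) = 0.0707, and exp(1.96 × 0.0707) = 1.149. The 95% interval is the estimate multiplied or divided by 1.149.
- Frequent event, narrowest case (3 per patient-year, 5 years, k = 0.5, SD 1.5): √(0.5667/1125) = 0.0224, giving a factor of 1.045.
- Rare event such as stroke, at an assumed 0.5 to 1 per 100 patient-years: 500 × 1 × 0.005 = 2.5 events to 500 × 5 × 0.01 = 25 events. With the Poisson form exp(1.96/√(events × SD²)), the factor runs from 3.45 down to 1.30.

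Under these assumptions a useful estimate is within reach for a frequent event and doubtful for stroke. A landmark analysis would use fewer participants and less follow-up, so these are best cases.

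**The case against.** **The number is a feasibility number.** This stands. A reader might infer that 500 is too small or was wrongly calculated. The documents do not support that, because no calculation exists. The defect is a stated purpose without an analysis.

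**The report is deliberately abbreviated.** This stands in part and lowers the weight of the point. But SAP 4.7.3 keeps both hematologic parameters and SCD events in focus, explains only the removal of PROMIS, and leaves SAP 4.5 unchanged. A reader might infer that the sponsor chose to drop the association. The documents do not say so.

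**It is not an endpoint.** The primary objective is to gather long-term data, the association is not in the effectiveness endpoint lists (Protocol 8.1.1.2, SAP 3.2), and Protocol 8.1 makes outcomes conditional on data being available. This also stands: it would be too strong to say that the study fails its primary objective. The commitment in Protocol 9.11.3 remains.

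**Each Hb group has its own pre-treatment rate, and readers can compare the tables.** The pre/post layout does help with baseline differences in event rate. It does not correct a grouping formed from post-treatment data. The comparison is also left to the reader, without an interval and for one event type.

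**Loss from dichotomising.** A reader might infer that the split discards a known share of the information. The formula φ(z)²/[p(1−p)] gives 64% retained at a 50:50 split and 49% at 20:80. It assumes a normal predictor and a linear effect, the documents give neither split, and it describes a fitted comparison, which the SAP does not plan. It does not measure this defect.

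**Conclusion.** The concern holds as a mismatch between purpose and analysis, together with a biased grouping in the one analysis that comes near the question. The mismatch follows from the text alone and needs no assumption. The grouping's dependence on testing is illustrated by a chance of entering the upper group that rises from 4–19% with one value to 22–63% with twelve. Those figures rest on the assumed SD, independence and no true change. Real values may be correlated, and a true Hb response would change the percentages.

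The net direction of the bias cannot be stated. Chance entry grows with follow-up, and transfusion around an event could move high-event participants into the upper group; the documents do not say how these combine. The point should be settled before results are interpreted. It carries no claim about participant safety or about the size of the study.

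**What to change.** Preferred: add a landmark count model to SAP 4.7.5.
- Predictor: continuous Hb change from pre-Oxbryta at a fixed early scheduled timepoint, for example month 6, with a rule for acute-visit values.
- Outcome: events after that timepoint, with log patient-years as offset and the end of follow-up stated. A negative binomial model is one suitable choice; the protocol names none.
- Adjustment: pre-Oxbryta event rate, age and hydroxyurea use, all already collected.
- Report: rate ratio per 1 g/dL with 95% interval for acute pain crisis, and for other listed events where counts allow.

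Keep Tables 15.5.3 and 15.5.4 as descriptive only, and reconcile their population: SAP 4.2.1 and 4.7.5 define the Hb groups on the Full analysis set, while the table titles say Safety analysis set.

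Cost: one model and one table from collected data. Participants without Hb at the landmark or not followed past it are lost, as are events before it. Enrolment is allowed after any time on drug, so late enrollees had to remain available until consent. Their time at risk needs an explicit rule, for example counting from the later of landmark and consent.

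Minimum alternative: state in SAP 4.5 and 4.7.3 that the association will not be estimated and that 500 is a feasibility number only, record the departure from Protocol 9.11.3, and draw no conclusion about the Hb-event relationship from the two tables. This costs a few sentences but leaves the stated purpose unmet.
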